#### The University of Texas Southwestern Medical Center at Dallas Institutional Review Board

#### Protocol

# Using High Definition transcranial Direct Current Stimulation to Treat Verbal Retrieval Deficits Secondary to Chronic Traumatic Brain Injury (HDtDCS-CTBI)

#### 1. Introduction and Purpose:

The pre-supplemental motor area (preSMA) has been shown to play a role in memory and word retrieval. Prior studies have suggested that neurostimulation targeting this region can improve word retrieval as well as other cognitive skills. Entraining the preSMA circuits with 10 sessions of neurostimulation could be used to improve cognitive functioning evaluated by EEG-based and neuropsychological measures. The purpose of this study is to examine the efficacy of high-definition transcranial direct current stimulation (HD-tDCS) to the preSMA region and its influence on EEG and neuropsychological measures in patients with chronic TBI. We also use MRI imaging to examine how baseline white matter integrity affects HD-tDCS therapeutic effects. The 3 aims of this study are 1) to determine HD-tDCS targeting pre-supplementary motor area (pre-SMA) modulatory effects on verbal retrieval function and synchronized brain activity using electroencephalography (EEG), 2) to use MRI imaging to examine how baseline white matter integrity affects HD-tDCS therapeutic effects. Herapeutic effects, and 3) to establish predictive models of HD-tDCS induced changes by integrating baseline EEG and MRI measures.

#### 2. Background:

High Definition transcranial Direct Current Stimulation (HD-tDCS) represents a safe, portable, and low-cost noninvasive brain stimulation technology to target more focused brain regions and modulate dysfunctional brain circuitry underlying neurocognitive symptoms. The pre-Supplementary Motor Area (pre-SMA) is part of the neural circuit underlying word retrieval functioning and can be more easily modulated by HD-tDCS than other deeper brain structures in the circuit. We have shown in pilot studies that adults with word retrieval impairment long after traumatic brain injury (TBI) can have enhancement of word retrieval from HD-tDCS targeting the pre-SMA. Immediately following stimulation, active HD-tDCS compared to sham was associated with significant improvement on a verbal (semantic) fluency task in a small sample of adults (N=25). We later combined neuropsychological and EEG measures in a case study of a patient with word retrieval impairment 3 years after a severe TBI, and found that HD-tDCS to the pre-SMA led to enhancement of verbal (phonemic) fluency (named 36 more items than baseline) and improved frontal EEG activity that lasted for 2 months. Thus, our preliminary work indicates HD-tDCS may have the potential to improve word retrieval functioning in those with chronic TBI and that HD-tDCS induced improvement could persist for 2 months

# 3. Study Procedures:

# **Overview and design**

We plan to recruit at least 24 English-speaking participants aged 18-85 years with a history of chronic TBI (> 1 year since injury), all of whom have problems with cognition. Participants will be randomized into an active HD-tDCS condition or a sham condition in order to assess the efficacy of HD-tDCS on improving cognition. The proposed study will measure response to HD-tDCS treatment over the preSMA region when compared to sham. Participants will receive two phases of 10 sessions of active stimulation (1 mA anodal HD-tDCS targeting preSMA for 20 min) or sham across 2 weeks. All participants will be blinded to their condition. EEG and neuropsychological tasks will be completed at

baseline, immediate follow-up after session 10, and a 2-month follow-up. Those participants randomized into the active or sham group will have the opportunity to return after 2 months and receive sham (if active first) or active (if sham first) treatment and will undergo the EEG and neuropsychological tests again immediately following the last HD-tDCS session and at a 2-month follow-up. With this design, we expect a 15% attrition rate and plan on enrolling ~30 adults to achieve our completed sample of 24.

# Sample size justification

Pre-study power analyses were conducted for the most power intensive phase of the study (Phase 1), using a clinically relevant effect size (Cohen's d = 1.20) derived from our prior studies. Holding 1- $\beta$ =0.8, and a=0.05, a sample size of 20 would provide sufficient power to identify true interaction effects (treatment \* time) across all neuropsychological outcome measures in the magnitude of f=0.27 (Cohen's d ≈ 0.54). Given that both our and other's research without intervention suggests that effect sizes tend to be larger in EEG compared to neuropsychological outcomes. We expect the effect size of EEG outcomes to be at least equivalent to neuropsychological outcomes. Still, we will perform an interim power analysis based on EEG data once half of the targeted recruitment is reached to ensure adequate statistical power. As the proposed sample size provides sufficient power to detect moderate effects for all outcomes, our study is well powered.

Below is a table summarizing the study visits followed by a detailed description of the procedures for each visit. It is a two Phase study. In Phase 1, participants will be randomized to active stimulation (1 mA anodal HD-tDCS targeting preSMA for 20 min) or sham and complete 13 visits. Then in Phase 2, participants who have been in the active group in Phase 1 will be invited to receive the active stimulation condition, and those who have been in the sham group in Phase 1 will be invited to receive the sham stimulation condition. Either way would involve 11 additional visits in the study.

TABLE 1. SUMMARY OF VISITS		
Phase 1	PROCEDURES	TIME
Visit 1	Pre-testing neuropsychological assessment/semantic EEG	3 hours
Visit 2	Pre-testing MRI scan	1 hour
Visits 3-11	HD-tDCS active or sham stimulation	30 minutes
Visit 12	HD-tDCS active or sham stimulation and post-testing neuropsychological assessment/semantic EEG	3 hours
Visit 13	8-week follow-up assessments/semantic EEG	3 hours
Phase 2		
Visits 14-22	HD-tDCS sham or active stimulation	30 minutes
Visit 23	HD-tDCS active stimulation and post-testing neuropsychological assessment/ semantic EEG	3 hours
Visit 24	8-week follow-up assessments/semantic EEG	3 hours

Transcranial Direct Current Stimulation (tDCS) is a non-invasive technique that requires the placement of several sensors (metal electrodes) on a special cap and saline gel on the participant's head. Very low levels of constant electrical current are delivered to specifically targeted areas of the brain via these electrodes. Contact quality and impedance levels (<10 kOhms) will be verified before each session. The same preparation is used for both active and sham conditions. After each session, subjects will be administered a standard post-treatment symptom questionnaire (e.g., assessing for skin irritation). Daily treatment lasting for 20 minutes (total of about 30-40 minutes including preparation) will be administered over 2 weeks (5 daily sessions each week), as scheduling allows. Session scheduling will depend on participant availability and availability in the lab. All treatment sessions will be held in [name] lab at UTDallas.

Assessment sessions, including the neuropsychological test battery and the Semantic Selection and Semantic Object Retrieval EEG tasks, will be completed at baseline, after intervention session 10, and at 2-month follow-up assessments. Each assessment session lasts approximately 3 hours. Specifically, the neuropsychological testing will take approximately 1 hour and will assess skills in the areas of word retrieval, episodic memory, processing speed, executive functions, and visuospatial organization. Participants will be asked to complete a few guestionnaires about emotional state and cognitive performance as well as completing computer tasks. These tests might be completed through in-person or remote online interviews. In addition, MRI scan will be obtained at baseline that include structural imaging and takes place at UTSW advanced imaging research center. Participants will also undergo event-related electroencephalography (EEG). The EEG procedure is a non-invasive technique that requires the placement of 64 sensors (metal electrodes) and saline gel on the scalp. The electrodes will record brain electrical activity while participants sit quietly in a chair and perform computer-based tasks. During the event-related EEG participants will be asked to react to visual stimuli shown on a screen using a button box. The EEG procedure will take place at the UT Dallas Callier Center for Communication Disorders, or Research and Operations Center West, both of which are in the laboratory of [name]. The EEG procedure takes nearly 2 hours.

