# 14. Biostatistics:

Mixed effects models will be used to evaluate if active HD-tDCS is associated with significant improvements over sham stimulation in neuropsychological assessments. Changes in performance from baseline to immediately post intervention (cognition in Hypothesis I) and baseline to the 2 month follow-up (Hypothesis II) will be assessed for each neuropsychological outcome measure. To test Hypotheses I and II, interaction effects among treatment group (active and sham) and time will be examined. Statistical significance will be set at a = .05. Covariates of interest include: age, sex, ethnicity, education, use of cholinesterase inhibitors, and assignment phase. Correlation coefficient across time is assumed around 0.6-0.7 based on the literature.

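### Phase 1 with 20 participants has about 25–36% power for a 0.54 SD treatment effect, not 80%; the f-to-d conversion halves the detectable effect, which is about 1.0–1.2 SD

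*Combined protocol and SAP*

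**What the plan says.** The Sample size justification (section 3) ties the calculation to one part of the trial: "Pre-study power analyses were conducted for the most power intensive phase of the study (Phase 1"). It starts from a large planning effect, "using a clinically relevant effect size (Cohen's d = 1.20) derived from our prior studies". With 1−β set at "0.8, and a=0.05, a sample size of 20 would provide sufficient power to identify true interaction effects" of treatment by time, it gives the size of that interaction as "in the magnitude of f=0.27 (Cohen's d ≈ 0.54"). It extends the statement to the EEG outcomes by expecting effects there at least as large, and ends: "As the proposed sample size provides sufficient power to detect moderate effects for all outcomes, our study is well powered".

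Section 14 (Biostatistics) supplies the other inputs: "Correlation coefficient across time is assumed around 0.6-0.7 based on the literature" and "Statistical significance will be set at a = .05". The Overview and design text schedules three Phase 1 assessments (baseline, after session 10, two months) and plans 24 completers from about 30 enrolled. The allocation ratio, the sidedness of the tests and the meaning of d for an interaction are not stated.

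**The concern.** The paragraph opens with d = 1.20 and closes with d of about 0.54, without saying how one leads to the other. The second figure is exactly 2 × 0.27. That is the conversion for a difference between two group means at one level, not for a difference between groups in change over time. Ten participants per arm would be very few to detect half a standard deviation with 80% power, even with a within-person correlation of 0.6–0.7.

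If the conversion is wrong, the protocol tells its readers that a moderate Phase 1 effect would be found four times in five when the real chance is nearer one in three. A null Phase 1 result could then be taken as evidence against a moderate effect on every outcome. The interim power analysis that the same paragraph plans on the EEG data would also be set against a wrong benchmark.

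**Working it through.** **Inputs.** From the documents: α = 0.05, power 80%, N = 20 (or 24 completers), f = 0.27, correlation r = 0.6–0.7. Assumed because not stated: 1:1 allocation (n = N/2 per arm), two-sided tests, and d read as the active-minus-sham difference in change in units of the outcome SD.

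**Step 1: reproduce the plan's f.** For a repeated-measures group-by-time interaction with 2 groups and m times, the noncentrality is λ = f²·N·m/(1−r), with m−1 and (N−2)(m−1) degrees of freedom. For m = 2 and r = 0.6, λ = 0.0729 × 20 × 2/0.4 = 7.29.

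| Times | r = 0.6 | r = 0.65 | r = 0.7 |
|---|---|---|---|
| m = 2 | 72.4% | 77.9% | 83.8% |
| m = 3 | 81.7% | – | – |

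So "in the magnitude of f=0.27" is a fair 80% figure for N = 20.

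**Step 2: convert f to a treatment effect.** Let both groups start equal and the active group change by Δ SD more than sham. The four interaction cell effects are ±Δ/4, so f = Δ/4 and Δ = 4f = 4 × 0.27 = 1.08 SD. With three times and an immediate or a sustained effect, f = 0.236Δ, so f = 0.27 means about 1.15 SD.

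**Step 3: confirm with the equivalent t-test.** For change scores, SE = √(2(1−r)·2/n). At r = 0.6 and n = 10 this is √(0.8 × 0.2) = 0.40. The noncentrality at Δ = 1.08 is 1.08/0.40 = 2.70, and 2.70² = 7.29, the λ of Step 1. Power at 1.08 SD is 72.4%, 77.9% and 83.8% for r = 0.6, 0.65 and 0.7, identical to the m = 2 row. At Δ = 0.54 the noncentrality is only 0.54/0.40 = 1.35.

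**Step 4: Phase 1 power and detectable effect.** The baseline-adjusted analysis uses SE = √((1−r²)·2/n) and one fewer degree of freedom. Ranges run from r = 0.6 to r = 0.7.

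| N | Analysis | Power at 0.54 SD | Effect with 80% power | Power at 1.20 SD |
|---|---|---|---|---|
| 20 | change | 24.8–31.5% | 1.19–1.03 SD | 81–91% |
| 20 | adjusted | 29.7–35.8% | 1.06–0.95 SD | 88–94% |
| 24 | change | 29.3–37.2% | 1.07–0.93 SD | 88–95% |
| 24 | adjusted | 35.1–42.4% | 0.96–0.86 SD | 94–98% |

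**Step 5: what 0.54 SD would need.** For 80% power in Phase 1, about 58 to 90 completers in total (58 with baseline adjustment at r = 0.7, 90 with change scores at r = 0.6). Alternatively, with N = 20, a correlation of about 0.91–0.92.

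**Step 6: link to the planning effect.** Under the correct conversion, d = 1.20 is f = 1.20/4 = 0.30, close to the stated 0.27. The two halves of the paragraph then agree, and 0.54 is the figure out of line.

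**The case against.** Four points can be made for the plan.

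- *The power calculation itself is sound.* N = 20, 80% and f = 0.27 reproduce, and d might be only a formal label for 2f. The first part stands: the fault lies in the conversion and in what is built on it. But the same paragraph uses d = 1.20 as a clinically relevant effect, and its conclusion about moderate effects treats 0.54 as lying on that scale. If d is only a label, that conclusion has no basis.
- *The proposed sample size may mean the 24 completers.* That is a natural reading, but power at 0.54 SD is then still at most 42%. If all 30 enrolled completed, it would be at most 52%.
- *The contrast in section 14 pools both phases.* This is the strongest point. With SE = √(0.25·2(1−r)·2/n), no carryover and everyone completing both phases, power at 0.54 SD is 72–84% with 20 and 81–90% with 24. However, the paragraph assigns its figure to Phase 1, Phase 2 is by invitation, and section 2 expects benefit that may last two months, which is when Phase 2 begins. If the active effect persisted fully, the arms would not differ in Phase 2 and the expected contrast would halve to 0.27 SD. At r = 0.6 and N = 20 the noncentrality is then 0.27/0.20 = 1.35, as in Phase 1 alone, and power falls back to 25–32%.
- *Nothing in the trial's conduct changes, and no rule for reading a null result is given.* Both are true. The figure is still wrong as written, and it is the stated basis for calling the study well powered.

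**Conclusion.** The concern holds. For Phase 1, the comparison the paragraph names, 20 participants give 25–36% power at a 0.54 SD difference in change, and 24 give 29–42%. Eighty per cent power is reached at about 0.95–1.19 SD with 20 and 0.86–1.07 SD with 24. The stated detectable effect is half of what the plan's own f implies (0.54 against 1.08 SD). The trial is powered for a large effect such as the pilot d = 1.20, not for a moderate one.

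This rests on 1:1 allocation, two-sided 5% tests, a correlation of 0.6–0.7, and d meaning the between-group difference in change in outcome-SD units. No Phase 1 variant examined reaches 80% at 0.54 SD; one-sided testing with 20 participants gives 37–49% on change or baseline-adjusted scores. Only the two-phase contrast without carryover comes near or above 80%.

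**What to change.** Keep the sample size and correct the paragraph. Delete the conversion to d of about 0.54 and the closing claim about moderate effects for all outcomes. In their place, state along these lines:

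*With 20 completers (10 per arm), two-sided 5% tests and a correlation across time of 0.6–0.7, Phase 1 has 80% power for a between-group difference in change from baseline to one follow-up of about 1.0–1.2 baseline SD (f about 0.27, where the difference is 4f); with 24 completers, about 0.9–1.1 SD. The lower ends apply to baseline-adjusted analysis and the upper ends to change scores.*

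Define d, and state the number of time points, the allocation ratio and the sidedness. The 4f rule is for two time points, which suits the planned baseline-to-one-follow-up tests; if a three-time interaction is meant, give that conversion instead. If the sponsor wants to claim power for moderate effects through the two-phase contrast, say so separately and state the assumptions on carryover and Phase 2 completion.

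The cost is the rewording of one paragraph and a less favourable detectable effect. No participants are added, and Phase 1 keeps 81–94% power at d = 1.20 with 20.

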Specifically, we will model each measure at the jth assessment time post-treatment from an individual subject in the ith treatment condition,  $y_{ij}$ , as  $y_{ij}=\mu 0+I(x)\cdot\mu ij+I(z)\cdot dij+eij0$ , where  $\mu 0$  is the baseline mean prior to random assignment to i=1,2 conditions (1- active, 2- sham); µij is the mean change from baseline for j=1,2 assessment times (1- immediate- [T1], 2- eight weeks [T2] post-treatment); I(x)is an indicator variable for phase 1; similarly, I(z) is an indicator for Phase 2 (sham-to-active vs activeto-sham conversion); and dij is the mean change from baseline for j =3,4 assessment times (3immediate- in phase 2, 4- eight weeks [T'2] post-treatment in phase 2). Additionally, eij0 is a random error term with *i*0=0,1,2,3,4, indicating baseline, post-assessment times for both Phases 1 & 2. Phase 1 & 2 errors between subjects are independent but positively correlated within subjects across time; additionally, a consequence of Phase 2 is that Phase 2 errors are positively correlated across the treatment conditions. Due to expected attrition, which will cause missingness in some (but not all) assessment times, and due to the complexity of the constraints, phases, and covariance parameterization in the linear mixed effects model above. all fixed-effect parameter estimates will be obtained by maximum likelihood and all covariance parameters for random effects will be obtained by restricted maximum likelihood (REML). All hypothesis tests will be based on t-statistics from a priori hypotheses, which are interaction contrasts of the form  $(\mu 1j + d1j)/2 - (\mu 2j + d2j)/2$  where j is understood to reflect the same assessment time regardless of phase (i.e., immediate post- OR 8 weeks post-treatment). The interaction contrast, shown above, reflects overall active HD-tDCS effects compared to sham. All analyses will be performed in SAS, R, and/or Matlab.

Mixed effects models will be used to evaluate if active HD-tDCS is associated with significant changes over sham stimulation in EEG measures. Changes from baseline to immediately post intervention (Hypothesis I - latency; Hypothesis II - magnitude) and then baseline to 2 month follow-up (Hypothesis III) will be assessed. To test Hypotheses I-III, interaction effects among treatment group (active and sham) and time will be examined. Statistical significance will be set at a = .05. Correlation coefficient across time is assumed around 0.6-0.7 based on the literature.

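### Phase 2 is a voluntary return with its condition fixed by the Phase 1 arm; it carries half of the efficacy contrast, and nothing planned would show whether guessed allocation shaped it

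*Combined protocol and SAP*

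**What the plan says.** **Entry and condition.** Section 3, Overview and design, says that participants "will have the opportunity to return after 2 months and receive sham (if active first) or active (if sham first) treatment". Section 3, Sample size justification, words Phase 2 as an invitation too, but with the same condition again: "participants who have been in the active group in Phase 1 will be invited to receive the active stimulation condition". It makes the matching statement for people first given sham. The visit load is equal: "Either way would involve 11 additional visits in the study". Table 1 describes the last Phase 2 treatment visit (Visit 23) as "HD-tDCS active stimulation and post-testing neuropsychological assessment/ semantic EEG", with no mention of sham. In the Section 14 model, the second indicator "is an indicator for Phase 2 (sham-to-active vs activeto-sham conversion", which is again a switch.

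**Blinding.** The only statement is in the design overview: "All participants will be blinded to their condition". A symptom questionnaire follows each stimulation session, but no treatment-guess item is described.

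**Analysis.** Section 14 bases its hypothesis tests on (μ1j + d1j)/2 − (μ2j + d2j)/2, where μ is the Phase 1 change, d is the Phase 2 change, and 1 and 2 are active and sham. It adds: "The interaction contrast, shown above, reflects overall active HD-tDCS effects compared to sham". Missing assessments are put down to attrition and handled by likelihood estimation. There is no separate Phase 1 result and no rule for people who do not enter Phase 2.

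**The concern.** A participant who completes Phase 1 chooses whether to come back for 11 more visits. If that person knows that Phase 2 is a switch, a belief about Phase 1 is also a belief about Phase 2. Someone who thinks they had active has less reason to return for sham, and someone who thinks they had sham has more. Those who return may also perform according to what they expect, on tests that respond to effort.

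Half of the efficacy estimate comes from this phase. If belief about allocation shapes Phase 2, the pooled contrast mixes a stimulation effect with an expectancy effect. Without a recorded guess or a Phase 1 result shown beside it, a reader could not tell the two apart.

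**Working it through.** **Inputs from the documents.** The contrast and a correlation across time of 0.6 to 0.7 (Section 14); N = 20, f = 0.27 (d ≈ 0.54), a prior-study d of 1.20, power 0.80 and α = 0.05 (Sample size justification); 24 completers (Overview and design); three Phase 1 assessments, at Visits 1, 12 and 13 (Table 1).

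**Assumptions.** Equal arms; an expectancy effect of 0.2 to 0.4 SD on the Phase 2 active-minus-sham difference. The documents give no value for the latter.

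**1. The plan's own figure.** For a repeated-measures interaction F test with two groups, λ = f²·N·m/(1 − ρ), with m − 1 and (N − 2)(m − 1) degrees of freedom. With m = 3 and ρ = 0.6, λ = 0.0729 × 20 × 3 / 0.4 = 10.935, and power is 0.82. The stated N of 20 reproduces. At ρ = 0.7, λ = 14.58 and power is 0.92. At N = 24 the two values are 0.89 and 0.96. With one follow-up time (m = 2), power is 0.72 to 0.84 at N = 20 and 0.81 to 0.90 at N = 24. The stated power therefore rests on Phase 1 and borrows nothing from Phase 2.

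One caution applies. If d = 0.54 is read as the difference between arms in change, in outcome SD units, a change-score t test with 12 per arm has power of only 0.29 (ρ = 0.6) to 0.37 (ρ = 0.7).

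**2. Weight of Phase 2.** (μ1j + d1j)/2 − (μ2j + d2j)/2 = ½(μ1j − μ2j) + ½(d1j − d2j). The half is exact. It is a weight in the contrast, not a share of the observations.

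**3. Pass-through.** A Phase 2 bias of b SD enters as b/2: 0.5 × 0.2 = 0.10 SD and 0.5 × 0.4 = 0.20 SD. Against d = 0.54 this is 19% and 37%; against d = 1.20 it is 8% and 17%.

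**4. Illustrative simulation.** No true effect, switch version, 12 per arm, ρ = 0.65, and Phase 2 entry of 50% (active first) against 90% (sham first), unrelated to outcome. Expectancy is added to Phase 2 active only. The contrast is formed from available mean changes, not from the full mixed model. All settings are assumed; entries are mean (SD) of the estimate over 4,000 runs.

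| Expectancy | Phase 1 alone | Phase 2 alone | Pooled |
|---|---|---|---|
| 0 | 0.00 (0.34) | 0.00 (0.44) | 0.00 (0.22) |
| 0.2 SD | −0.01 (0.33) | 0.21 (0.44) | 0.10 (0.22) |
| 0.4 SD | 0.00 (0.34) | 0.41 (0.43) | 0.20 (0.21) |

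The first row shows that very unequal uptake alone does no harm. The others show that the bias reaches the pooled contrast at half size and leaves Phase 1 untouched.

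**5. Effect on the test.** With a pooled SD of 0.22, a normal approximation puts the shifts at 0.10/0.22 ≈ 0.45 and 0.20/0.22 ≈ 0.91 standard errors. The two-sided false-positive rate then rises from 5% to about 7% and 15%.

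**The case against.** A reader might infer that the invitation itself tells participants their condition and so contradicts the blinding statement. The documents do not support that. The sentences in Section 3 set out who gets what for readers of the protocol; they are not an invitation script. Both arms are invited, the extra visits are equal, preparation is the same for active and sham, and blinding is stated for everyone. The plan is silent on how the invitation is worded, which is a gap and not a contradiction.

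A reader might also infer that the offer could unblind the 8-week Phase 1 assessment. The sample size section has participants complete 13 visits before the invitation, and Table 1 places the 8-week assessment at Visit 13, inside Phase 1. On the described sequence, that assessment is finished first.

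Further points stand in part. The design overview also says that participants receive two phases, and initial consent may cover both; the consent text is not among the documents available here. For the same reason, what participants know about a switch cannot be seen. The likelihood model uses Phase 1 scores, so it handles entry to the extent that those scores explain it. It cannot handle the part of a belief that is neither recorded nor reflected in the scores. Listing assignment phase as a covariate does not help either, because it absorbs a shift common to both conditions, not one tied to perceived active treatment.

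**Conclusion.** The concern holds in a limited form. Optional entry, a condition fixed by the Phase 1 arm and a half weight in the tested contrast are all on the page. So is the absence of any means to see whether perceived allocation influenced the result. The size, 0.10 to 0.20 SD in the pooled contrast, rests wholly on the assumed expectancy effect and on its applying across Phase 2 participants. No size is given for guess-driven entry, since that needs a further link between guess and unobserved outcome. It would be wrong to conclude that unequal uptake biases the contrast by itself.

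The contrast is written out for the neuropsychological model; the EEG paragraph does not repeat it, so its use there is an inference. The d terms also have no settled meaning while Section 3 and Section 14 describe a switch, the sample size section describes a repeat, and Table 1 lists only active at Visit 23. This point takes no view on which is intended. The change is worth making because it is cheap and because a guess not recorded at the time cannot be recovered.

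**What to change.** First, reconcile the design overview, the sample size section, Table 1 (Visit 23) and the Section 14 indicator on the Phase 2 condition. Then:

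1. Add one item (active / sham / don't know) to the existing post-session questionnaire after session 10 of each phase (Visits 12 and 23). Fix its position relative to outcome testing, the same for everyone.
2. Report the randomised Phase 1 contrast, μ1j − μ2j, beside the pooled contrast, together with Phase 2 uptake by arm and the guess results.
3. State that the Phase 2 invitation is identical for both arms and names no condition, and that allocation is not disclosed before Visit 24.

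The cost is one questionnaire item at two visits, some protocol wording and a few lines of reporting, with no added visits. There are two downsides. The item could slightly prime expectancy if it is asked before testing. The Phase 1 estimate is also less precise than the pooled one (SD about 0.34 against 0.22 in the illustration), so it should be read as a check on the pooled result and not expected to reach significance whenever the pooled one does.

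### The paragraph introducing Table 1 keeps each arm on its Phase 1 condition in Phase 2, and the Visit 23 row lists active only; both contradict the switch in the design overview and the analysis model

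*Combined protocol and SAP*

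**What the plan says.** - **Section 3, Overview and design.** After two months participants may return to "receive sham (if active first) or active (if sham first) treatment". This is a switch in both arms.
- **Sample size justification, paragraph introducing Table 1.** The Phase 2 instruction for the active arm is: "participants who have been in the active group in Phase 1 will be invited to receive the active stimulation condition". The other arm is treated in the same way, staying on its original condition, so neither arm switches.
- **Table 1, Phase 2.** Visits 14-22 read "HD-tDCS sham or active stimulation". Visit 23 reads "HD-tDCS active stimulation and post-testing neuropsychological assessment/ semantic EEG", with no mention of sham. The matching Phase 1 row, Visit 12, reads "HD-tDCS active or sham stimulation and post-testing neuropsychological assessment/semantic EEG".
- **Section 14, Biostatistics.** The Phase 2 term is defined by a switch: "I(z) is an indicator for Phase 2 (sham-to-active vs activeto-sham conversion". All hypothesis tests use the contrast (μ1j + d1j)/2 − (μ2j + d2j)/2, where μ is the Phase 1 change and d the Phase 2 change. The section presents it as the overall active-versus-sham effect. It models an observation "from an individual subject in the ith treatment condition" but does not say outright what i means once a participant has changed condition.

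**The concern.** These sentences tell staff which stimulation to give, and they cannot all be followed. A site working from the Sample size justification would give both arms the opposite Phase 2 condition from the one the design overview promises, and sham-first participants would never receive active stimulation. A site working from the Visit 23 row would give participants on Phase 2 sham an active session at the visit where their immediate post-test takes place.

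The conflict also reaches the analysis. The a priori contrast pools both phases, so its meaning depends on the Phase 2 condition delivered being the one modelled.

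**Working it through.** **1. The texts side by side**

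| Place | Active-first group, Phase 2 | Sham-first group, Phase 2 |
|---|---|---|
| Overview and design | sham | active |
| Sample size justification, paragraph before Table 1 | active | sham |
| Table 1, Visits 14-22 (sessions 1-9) | sham or active, not assigned | sham or active, not assigned |
| Table 1, Visit 23 (session 10) | active | active |
| Section 14, Phase 2 indicator | sham | active |

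The overview and section 14 agree. The Sample size justification sentence is the reverse of both. Visit 23 conflicts with the overview for the active-first group and with the Sample size justification sentence for the sham-first group. All of this is current text, and no redaction or broken table accounts for it.

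**2. The plan's own sample size**

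Inputs: N = 20, f = 0.27, α = 0.05, power 0.8 (Sample size justification); correlation across time 0.6-0.7 (section 14). For a group-by-time interaction with g = 2 groups and m = 3 times, λ = f²Nm/(1 − ρ) = 0.27² × 20 × 3/(1 − 0.6) = 10.94 on 2 and 36 degrees of freedom. Power is 0.817, so N = 20 is reproduced. The calculation concerns Phase 1 only and does not depend on the Phase 2 allocation.

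**3. Sessions affected**

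Phase 2 has 9 sessions (Visits 14-22) plus 1 (Visit 23), so 10 per participant. If all 24 completers enter Phase 2, that is 24 × 10 = 240.
- Sample size justification sentence: all 240 differ from the overview.
- Visit 23 row alone: 1 session in 10 for each Phase 2 sham participant. With 1:1 allocation (an assumption; the plan gives no ratio) that is 12 × 1 = 12, and 12/240 = 5%.

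**4. What the contrast estimates**

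Let τ be the active effect on change from baseline, and τ₂ the effect present after a second active course. Practice and period effects common to both arms cancel. The plan gives no value for τ₂, so a range is shown.

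*Delivered without a switch, coded as a switch.* d1j comes from the sham-first group, which received sham again (0). d2j comes from the active-first group, which received active again (τ₂). The contrast is (τ + 0)/2 − (0 + τ₂)/2 = (τ − τ₂)/2:

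| τ₂ | 0.5τ | τ | 1.5τ |
|---|---|---|---|
| Contrast | 0.25τ | 0 | −0.25τ |

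*Delivered without a switch, coded as delivered.* The cancellation disappears, but the contrast becomes purely between-subject. With compound symmetry, n per sequence, unit variance, complete data and no carryover, its variance is:
- with the switch: (1 − ρ)/n;
- without it, raw change from baseline: 3(1 − ρ)/n, which is 3.0 times as large;
- without it, baseline-adjusted: (1 − ρ)(1 + 2ρ)/n, which is 2.2 times as large at ρ = 0.6 and 2.4 times at ρ = 0.7.

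**5. The index i under the intended switch**

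Let c_j be the fraction of the first-course effect still present at the Phase 2 assessment (assumed; not in the plan). The Phase 2 assessments fall at least 8 + 2 = 10 and 10 + 8 = 18 weeks after the first course ends. Section 2, Background, raises persistence to 2 months.
- i is the condition received: (τ + τ)/2 − (0 + c_jτ)/2 = τ(1 − c_j/2).
- i is the randomised arm: (τ + c_jτ)/2 − (0 + τ)/2 = c_jτ/2.

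| c_j | 0 | 0.25 | 0.5 | 1 |
|---|---|---|---|---|
| Condition received | 1.00τ | 0.875τ | 0.75τ | 0.50τ |
| Randomised arm | 0 | 0.125τ | 0.25τ | 0.50τ |

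Only the first reading gives the active-versus-sham effect the section describes.

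**The case against.** The intended design can be recovered: the overview and the model agree on the switch, and the conflicting text is a visit summary that looks like a drafting slip. Visit 23 is one cell, and the row above it allows either condition. Phase 2 is optional, so 240 sessions is a ceiling. The cancelling contrast needs two failures together: delivery by the wrong sentence and coding by the opposite rule. The meaning of i is a notation question separate from the contradiction, and section 14 also introduces i in connection with random assignment, which points towards the randomised arm. Carryover arises even under the correct design.

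Much of this is fair, and it limits what can be claimed. The contrast values are conditional, and nothing in the documents shows what was delivered. The i and carryover figures show why a definition is needed; they do not measure the contradiction. The random-assignment cue is real, but it still labels i as active or sham, and the stated meaning of the contrast requires the condition received.

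The core point stands. That a reader can infer the intended design does not make the instruction safe: the paragraph before Table 1 says, arm by arm, which stimulation to give, and it is wrong for both arms.

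**Conclusion.** The concern holds and must be fixed. The plan's Phase 2 instructions contradict each other, and the Sample size justification sentence and the Visit 23 row are the text in error. Confidence in the textual conflict is high.

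Its size in delivery is up to 240 sessions for the sentence, and about 12 of 240 for the Visit 23 row alone under 1:1 allocation; both figures assume that all 24 completers enter Phase 2. Its size in the analysis depends on what is delivered and how it is coded: from a loss of precision (variance 2.2 to 3.0 times as large) to a contrast that is zero or reversed. Those figures rest on the assumed values of τ₂, the correlation structure and complete data. The Phase 1 comparison and its sample size are not affected.

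**What to change.** 1. **Sample size justification, paragraph before Table 1:** state that the Phase 1 active group is invited to receive sham in Phase 2, and the Phase 1 sham group is invited to receive active.
2. **Table 1, Visit 23:** list sham or active stimulation, matching Visits 14-22 and the Phase 1 row for Visit 12.
3. **Section 14:** state that i in d_ij is the condition received in that phase, so d1j comes from the sham-first group and d2j from the active-first group.

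This costs a wording amendment to one sentence, one table row and one definition, with no new data, visits or participants. It does not remove carryover. The Phase 1 contrast μ1j − μ2j is free of both the allocation conflict and carryover, and can be reported beside the combined contrast.
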